### **12.1. Treatment of Missing and Spurious Data**

See general definitions in chapter 5.4.

### **12.2. Exclusion of Particular Information**

See general definitions in chapter 5.5.

No data are excluded from the specified analysis set and variables.

### **12.3. Descriptive Analyses**

For specification "Notes = descriptive", see general definitions in chapter 5.1.

### **12.4. Hypotheses & Statistical Tests**

There are no pre-defined statistical hypotheses.

## 13. General Assessments - Implantation

### CIP chapter 7.5 Further data of interest

During implantation and follow-ups additional data on safety, performance and usability of the Renamic Neo system and accessories will be collected.

- Use and assessment of PSA functionality (sensing, pacing and impedance tests)
- Success of adequate programming of the implant
- Evaluation of interrogation of the implant including RF telemetry
- Overall assessment of device hardware or software performance including battery use
- Data export evaluation (used connectivity, destination, printing)

...

### 13.1. Analysis Set and Data Selection

All analyses are performed for patients in the implantation analysis set using a specific data selection before / at implantation.

Data file, identifier	Notes	Variable name	Variable label	Variable level	Nominal values
patient display id full & autom SVTYP					
general assessments	No report	autom SVTYP	Visit type	nominal	
 
○ Implantation
 
○ Pre-hospital discharge follow-up (PHD)
 
○ Regular follow-up after PHD
 

 analysis set imp SAR = Yes  
 Data selection for general assessments with autom SVTYP = implantation

Used Programmer Features: Implant

Data file, identifier patient display id full & autom SVTYP	Notes	Variable name	Variable label	Variable level	Nominal values
general assessments (see Analysis Set and Data Selection)	descriptive	QSPGHAS	Programmer head (PGH) telemetry	nominal	 used successfully  used, but not successfully
	descriptive#	QSPGHPRB	Did you notice any problem* (see definition above) with usage of programmer head telemetry	nominal	 Yes, with Adverse Event  Yes, without Adverse Event  No problem detected
	descriptive with "not used" and "not available..." handled as missing	QSRFTAS	RF telemetry for implant interrogation	nominal	 used successfully  used, but not successfully  not used  not available for implant by default
	descriptive#	QSRFTPRB	Did you notice any problem* (see definition above) with usage of RF telemetry for implant interrogation	nominal	 Yes, with Adverse Event  Yes, without Adverse Event  No problem detected
	descriptive with "not used" handled as missing	QSSAAS	Sensing amplitude	nominal	 used successfully  used, but not successfully  not used
	descriptive#	QSSAPRB	Did you notice any problem* (see definition above) with usage of sensing amplitude	nominal	 Yes, with Adverse Event  Yes, without Adverse Event  No problem detected
	descriptive with "not used" handled as missing	QSPTAS	Pacing threshold	nominal	 used successfully  used, but not successfully  not used
	descriptive#	QSPRPRB	Did you notice any problem* (see definition above) with usage of pacing threshold	nominal	 Yes, with Adverse Event  Yes, without Adverse Event  No problem detected
	descriptive with "not used" handled as missing	QSPITAS	Impedance test	nominal	 used successfully  used, but not successfully  not used
	descriptive#	QSPITPRB	Did you notice any problem* (see definition above) with usage of impedance test	nominal	 Yes, with Adverse Event  Yes, without Adverse Event  No problem detected
	descriptive with "not used" OR VectorOpt not available ..." handled as missing	QSDFPAS	LV Pacing threshold and PNS measurement for different polarities	nominal	 used successfully  used, but not successfully  not used  VectorOpt not available for CRT implant
	descriptive#	QSDFPPRB	Did you notice any problem* (see definition above) with usage of LV Vector Opt function	nominal	 Yes, with Adverse Event  Yes, without Adverse Event  No problem detected
	descriptive with "not done" handled as missing	QSPRGAS	Programming of the implant	nominal	 device successfully programmed  device not successfully programmed  not done
	descriptive#	QSPRGPRB	Did you notice any problem* (see definition above) with usage of programming of the implant function	nominal	 Yes, with Adverse Event  Yes, without Adverse Event  No problem detected
	descriptive with "not used" handled as missing	QSDFTAS	DFT (Defibrillation Threshold Testing) if performed in routine care	nominal	 used successfully  used, but not successfully  not used
	descriptive#	QSDFTPRB	Did you notice any problem* (see definition above) with usage of DFT	nominal	 Yes, with Adverse Event  Yes, without Adverse Event  No problem detected

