8.1.2 Measures taken to minimize or avoid bias

The study will be conducted according to BIOTRONIK's internal Standard Operating Procedures to minimize and avoid potential bias.

The study does not require randomization or blinding as it does not require a control group.

It will be conducted at up to 10 sites to avoid a hospital-specific bias caused by the specific hospital environment or the programmer user. A maximum number of 30 programmer use cases (implantations and FUs) per site is defined to avoid site specific bias in case of high enrollment rates of single sites. Exemptions will be communicated in written form in case enrollment is too slow.

Furthermore, the number of implantations and follow-ups for a specific implant type is defined for the whole study to avoid an unbalanced usage of specific, implant related programmer functions. The 50 implantation and 100 follow-up (including PHD) cases should be distributed as follows:

- IPG, ICD: ~15 implantations and ~20 follow-up cases for each
- ICM: ~20 follow-up cases
- CRT-D /-P: ~20 implantations and ~40 follow-up cases for both combined

As no PSA measurements will be performed for ICMs no implantation cases or PHDs shall be performed for ICMs, but only follow-up cases.

A survey for implantation and follow-up numbers for each implant type is implemented in the iMedNet system. The sponsor will immediately inform all sites whenever the required number of a certain implant type has been reached.

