11.2 Sample size

No hypotheses can be pre-specified for this clinical investigation, which is completely exploratory.

This clinical investigation should be able to identify unforeseen safety problems. While it is unlikely that the number of ADEs or DDs will be sufficient for inferential statistical conclusions, a discussion of the types of events and of the circumstances of their appearance might reveal indicators for hidden risks and trigger further dedicated investigations or statistical tests to substantiate such findings.

Unforeseen safety problems are more likely related to software problems between Renamic Neo and implanted devices but less likely to hardware problems of the Renamic Neo. Thus, the sample size is related to use cases per implantation, pre-hospital discharge, and follow-up but not to the total number of Renamic Neo devices.

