# If preceding variable = "used successfully" or "device successfully programmed" then impute missing data with " Used successfully".

Data file, identifier patient display id full & autom SVTYP	Notes	Variable name	Variable label	Variable level	Nominal values
general assessments (see Analysis Set and Data Selection)	case listing for QSPGHAS = used, but not successfully OR QSPGHPRB = Yes, with Adverse Event OR QSPGHPRB = Yes, without Adverse Event including programmer serial number DIPRGSNR (see chapter15.1)	COPGHAS	Please specify reason for unsuccessful use of programmer head telemetry	text	...
	case listing for QSRFTAS = used, but not successfully OR QSRFTPRB = Yes, with Adverse Event OR QSRFTPRB = Yes, without Adverse Event including programmer serial number DIPRGSNR (see chapter15.1)	CORFTAS	Please specify reason for unsuccessful use of RF telemetry for implant interrogation	text	...
	case listing for QSSAAS = used, but not successfully OR QSSAPRB = Yes, with Adverse Event OR QSSAPRB = Yes, without Adverse Event including programmer serial number DIPRGSNR (see chapter15.1)	COSAAS	Please specify reason for unsuccessful use of sensing amplitude	text	...
	case listing for QSPTAS = used, but not successfully OR QSPRPRB = Yes, with Adverse Event OR QSPRPRB = Yes, without Adverse Event including programmer serial number DIPRGSNR (see chapter15.1)	COPTAS	Please specify reason for unsuccessful use of pacing threshold	text	...
	case listing for QSPITAS = used, but not successfully OR QSPITPRB = Yes, with Adverse Event OR QSPITPRB = Yes, without Adverse Event including programmer serial number DIPRGSNR (see chapter15.1)	COPITAS	Please specify reason for unsuccessful use of impedance test	text	...
	case listing for QSDFPAS = used, but not successfully OR QSDFPPRB = Yes, with Adverse Event OR QSDFPPRB = Yes, without Adverse Event including programmer serial number DIPRGSNR (see chapter15.1)	CODFPAS	Please specify reason for unsuccessful use of LV Vector Opt function	text	...
	case listing for QSPRGAS = used, but not successfully OR QSPRGPRB = Yes, with Adverse Event OR QSPRGPRB = Yes, without Adverse Event including programmer serial number DIPRGSNR (see chapter15.1)	COPRGAS	Please specify reason for unsuccessful programming of the implant	text	...

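### Case numbers are set per implant type, but the telemetry, test and programming results are specified only pooled over types, and uses per type are not reported

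*SAP*

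**What the plan says.** **Design.** Protocol 8.1.2, on avoiding bias, introduces numbers per implant type with "The 50 implantation and 100 follow-up (including PHD) cases should be distributed as follows". The entries are "IPG, ICD: ~15 implantations and ~20 follow-up cases for each", "ICM: ~20 follow-up cases" and "CRT-D /-P: ~20 implantations and ~40 follow-up cases for both combined". The stated reason is "to avoid an unbalanced usage of specific, implant related programmer functions". Protocol 11.2 adds: "Unforeseen safety problems are more likely related to software problems between Renamic Neo and implanted devices".

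**Analysis.** SAP 13.1 defines the set for the general assessments at implantation: "All analyses are performed for patients in the implantation analysis set using a specific data selection before / at implantation". Its table Used Programmer Features: Implant asks for one frequency per item: programmer-head (PGH) telemetry, RF telemetry, sensing, threshold, impedance, LV VectorOpt, programming and defibrillation threshold testing. SAP 14.1 repeats chapter 13 for the pre-hospital discharge and follow-up set. For most items, the answers for not used, not done or not available are treated as missing. PGH telemetry has no such answer.

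**Listings.** Unsuccessful uses and reported problems are listed case by case with a free-text item, for example "Please specify reason for unsuccessful use of RF telemetry for implant interrogation". The programmer serial number `DIPRGSNR` is added; implant type and model are not.

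**Subgroups.** SAP 7 derives `subgroup device type SAR`, but chapters 8 to 16 do not call it. SAP 5.6, repeating protocol 11.9, promises a look by IPG, ICD, CRT and ICM for potentially critical events only, without defining the term. SAP 5.1 shows table templates both overall and split by implanted device type, but does not say which variables get the split.

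**The concern.** The sampling is organised by implant type because programmer functions depend on the implant, yet the results for those functions ignore type. If success differs between types, a pooled percentage describes the planned case mix and not any one implant family. A problem confined to one family then appears as a small overall percentage. Protocol 11.2 considers the interface between programmer software and implant the likelier source of unforeseen safety problems, but the listings add an identifier of the programmer hardware and none of the implant.

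The point concerns the performance results of SAP chapters 13 and 14, not the adverse device effect and device deficiency endpoints of chapters 10 and 11. At stake is whether the report can show performance for each implant type the study set out to cover.

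**Working it through.** **1. The plan's own figures.** Protocol 11.2.1 and 11.2.2 give the chance of seeing at least one, two or three events at a true rate of 5%. With X binomial(n, 0.05):

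| n | P(X ≥ 1) | P(X ≥ 2) | P(X ≥ 3) | Protocol |
|---|---|---|---|---|
| 50 | 92.3% | 72.1% | 46.0% | 92 / 72 / 46% |
| 100 | 99.4% | 96.3% | 88.2% | 99 / 96 / 88% |

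These reproduce. They refer to total case numbers. The plan gives no figure by implant type.

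**2. Inputs (protocol 8.1.2).** Implantation: IPG 15, ICD 15, CRT 20, total 50. Follow-up including pre-hospital discharge: IPG 20, ICD 20, ICM 20, CRT 40, total 100. All are approximate targets.

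**3. Dilution.** If failures occur only in type k, at rate f, the pooled rate is f × n_k / N, so the dilution factor is N / n_k. This assumes that the targets are met and every case enters the denominator.

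| Setting | Type | N / n_k | Factor |
|---|---|---|---|
| Implantation | IPG, ICD | 50 / 15 | 3.3 |
| Implantation | CRT | 50 / 20 | 2.5 |
| Follow-up | IPG, ICD, ICM | 100 / 20 | 5.0 |
| Follow-up | CRT | 100 / 40 | 2.5 |

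**4. Illustrations under the same assumptions (exact 95% intervals).**

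- Two failures, both in ICD implantations: 2/50 = 4% pooled, 2/15 = 13.3% in ICDs (1.7% to 40.5%).
- Two failures at follow-up, both in one type with 20 cases: 2/100 = 2% pooled, 2/20 = 10% in that type (1.2% to 31.7%).
- Eight failures at follow-up, all in CRT: 8/100 = 8% pooled, 8/40 = 20% in CRT (9.1% to 35.6%).

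**5. When non-users leave the denominator.** If ICM cases drop out of a function such as the pacing threshold test (an assumption), the follow-up total is 80. The factor becomes 80/20 = 4 for IPG and ICD and 80/40 = 2 for CRT. For a function used in CRT only, such as LV VectorOpt, the other types drop out and the factor is about 1. PGH telemetry keeps the full factor of step 3 if it is recorded in every case.

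**6. Can a reader rebuild the rate by type?** The listings supply failures, and linking patient ID to the device log would give their type. The number of uses per function and type is in no planned output. The nearest table, device model in SAP 15.1, counts patients by model, not uses of a function. It could at most approximate the denominator for an item recorded in every case.

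**7. What a split can show.** At a 5% rate within a type, the chance of at least one event is 1 − 0.95^n: 53.7% for n = 15, 64.2% for n = 20 and 87.1% for n = 40. Rows by type describe; they do not establish absence of a problem.

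**The case against.** The strongest reply is that the plan relies on individual review. With few expected events, protocol 11.2 looks to discussion of single events and their circumstances, and SAP 13.1 lists unsuccessful uses and problems one by one. Patient ID links each to the device log. A telemetry or programming malfunction can also be a device deficiency under protocol 18.3 and so be adjudicated and listed under SAP 10 and 11, and SAP 5.6 covers potentially critical events by type. There is no hypothesis and no pass/fail criterion. This stands, and it limits the point to the summary tables and the content of the listings. It does not supply denominators, and an unsuccessful session without harm need not count as a critical event.

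A second reply is that the case numbers serve coverage and balance, and that protocol 8.1.2 promises no estimates by type. This also stands. A reader might infer that the SAP breaches the protocol; it does not. The set definition in SAP 13.1 does not exclude subgroup tables either, and SAP 13.3 refers to SAP 5.1, which contains the split template. The gap is that nothing assigns that template to these items.

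A reader might also infer that type-specific failures would be hidden. The listings contradict that, with one drafting exception. The programming listing selects `QSPRGAS` by the answer *used, but not successfully*, which is not one of that item's answers. As written, a failed programming is listed only if the accompanying problem item is also positive.

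**Conclusion.** The point holds as a gap in reporting. The implant-related performance results are specified pooled, the derived device-type variable is left unused, and uses per type are not reported. Where all types use a function, dilution of a one-type failure is 2.5- to 3.3-fold at implantation and 2.5- to 5-fold at follow-up. This rests on the approximate case numbers being met, every case entering the denominator, and the failure being confined to one type.

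A reader might infer a dilution of three-fold or more throughout. CRT, the largest group in both settings, is at 2.5, and the factor falls further wherever non-users are set to missing. Nor do the documents support a claim that any endpoint or decision is compromised: the study is exploratory, and no rule rests on these percentages. The change is worth making because it is inexpensive and lets the report show performance by the strata used for sampling.

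**What to change.** 1. In SAP 13.3 and 14.1, keep the pooled tables and add, in the SAP 5.1 subgroup format, the success and problem items of Used Programmer Features: Implant by implant type, with the number of uses per type. Mark these rows as descriptive because the groups are small.
2. Map the levels of `subgroup device type SAR` (CRT, CRT-P, ICD, ICM, IPG) to the protocol 8.1.2 groups: IPG, ICD, CRT-D and CRT-P combined, and ICM at follow-up only.
3. Add implant type and model next to `DIPRGSNR` in the case listings. Take the model directly from the device log. The SAP 15.1 footnote deriving the device model joins pacemaker and ICD with AND, so read literally it drops both.
4. Align the selection for the programming listing with the answers that `QSPRGAS` actually has.

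The cost is SAP wording, a mapping step and extra table rows and listing columns. Data and table format already exist. No endpoint, sample size or decision rule changes.

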# If preceding variable = "used successfully" or "device successfully programmed" then impute missing data with " Used successfully".

Data file, identifier patient display id full & autom SVTYP	Notes	Variable name	Variable label	Variable level	Nominal values
general assessments (see Analysis Set and Data Selection)	case listing for QSPGHAS = used, but not successfully OR QSPGHPRB = Yes, with Adverse Event OR QSPGHPRB = Yes, without Adverse Event including programmer serial number DIPRGSNR (see chapter15.1)	COPGHAS	Please specify reason for unsuccessful use of programmer head telemetry	text	...
	case listing for QSRFTAS = used, but not successfully OR QSRFTPRB = Yes, with Adverse Event OR QSRFTPRB = Yes, without Adverse Event including programmer serial number DIPRGSNR (see chapter15.1)	CORFTAS	Please specify reason for unsuccessful use of RF telemetry for implant interrogation	text	...
	case listing for QSSAAS = used, but not successfully OR QSSAPRB = Yes, with Adverse Event OR QSSAPRB = Yes, without Adverse Event including programmer serial number DIPRGSNR (see chapter15.1)	COSAAS	Please specify reason for unsuccessful use of sensing amplitude	text	...
	case listing for QSPTAS = used, but not successfully OR QSPRPRB = Yes, with Adverse Event OR QSPRPRB = Yes, without Adverse Event including programmer serial number DIPRGSNR (see chapter15.1)	COPTAS	Please specify reason for unsuccessful use of pacing threshold	text	...
	case listing for QSPITAS = used, but not successfully OR QSPITPRB = Yes, with Adverse Event OR QSPITPRB = Yes, without Adverse Event including programmer serial number DIPRGSNR (see chapter15.1)	COPITAS	Please specify reason for unsuccessful use of impedance test	text	...
	case listing for QSDFPAS = used, but not successfully OR QSDFPPRB = Yes, with Adverse Event OR QSDFPPRB = Yes, without Adverse Event including programmer serial number DIPRGSNR (see chapter15.1)	CODFPAS	Please specify reason for unsuccessful use of LV Vector Opt function	text	...
	case listing for QSPRGAS = used, but not successfully OR QSPRGPRB = Yes, with Adverse Event OR QSPRGPRB = Yes, without Adverse Event including programmer serial number DIPRGSNR (see chapter15.1)	COPRGAS	Please specify reason for unsuccessful programming of the implant	text	...
	case listing for QSDFTAS = used, but not successfully OR QSDFTPRB = Yes, with Adverse Event OR QSDFTPRB = Yes, without Adverse Event including programmer serial number DIPRGSNR (see chapter15.1)	CODFTAS	Please specify reason for unsuccessful use of DFT	text	...

Accuracy of PSA Measurements

The analyses specified in this sub-chapter have to be performed for the implantation analysis set only.

Data file, identifier patient display id full & autom SVTYP	Notes	Variable name	Variable label	Variable level	Nominal values
general assessments (see Analysis Set and Data Selection)	descriptive with "no comparison possible" handled as missing	DUPSAAS	Are PSA measurement results (sensitivity, pacing threshold, impedance) sufficiently accurate, compared to the measurement results of the implanted device	nominal	o Yes o No o no comparison possible

Data file, identifier patient display id full & autom SVTYP	Notes	Variable name	Variable label	Variable level	Nominal values
general assessments (see Analysis Set and Data Selection)	case listing for DUPSAAS = No OR DUPSAAS = no comparison possible including programmer serial number DIPRGSNR (see chapter15.1)	COPSAAS	Please specify No / no comparison possible	text	...

Used Programmer Features: Data export

Data file, identifier patient display id full & autom SVTYP	Notes	Variable name	Variable label	Variable level	Nominal values
general assessments (see Analysis Set and Data Selection)	descriptive	PRDEXP	Was data export performed	nominal	o Yes o No
		DULAN01	NEW: Connectivity: LAN	nominal	o Yes o No
		DUWLAN01	NEW: Connectivity: WLAN	nominal	o Yes o No
		DUUSB01	NEW: Connectivity: USB	nominal	o Yes o No
		QSCNNAS	Was connectivity used successfully	nominal	o Yes o No
		QSCNNPRB #	NEW: Connectivity: Did you notice any problem* (see definition above)	nominal	o Yes o No problem detected
		DUNTSH	NEW: Data export: Network share (for EHR)	nominal	o Yes o No
		DUUSBS	NEW: Data export: USB stick	nominal	o Yes o No
		DUOTH	NEW: Data export: Other	nominal	o Yes o No
		PRDEXPAS	Was data export successful	nominal	o Yes o No
		QSDEXPPR #	NEW: Data export: Did you notice any problem* (see definition above)	nominal	o Yes o No problem detected

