7.5 Further data of interest

General information

- Patient demographics and medical history
- Implant type and model, all other implanted devices
- Lead model and programmer software version

During implantation and follow-ups additional data on safety, performance and usability of the Renamic Neo system and accessories will be collected.

- Use and assessment of PSA functionality (sensing, pacing and impedance tests)
- Success of adequate programming of the implant

- Evaluation of interrogation of the implant including RF telemetry
- Overall assessment of device hardware or software performance including battery use
- Data export evaluation (used connectivity, destination, printing)
- Export of programmer data export files that document the performed use case for evaluation at the sponsor
- Information on additionally used accessories or other implanted cardiac devices

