### 10.2. Variables

#### Adjudicated Adverse Device Effects / Device Deficiencies

Data file, identifier record id	Notes	Variable name	Variable label	Variable Level	Nominal values
internal adjudication	Case listing for AETYP = AE	AETYP	Type of event	nominal	o AE o DD
		AESTDT	Onset date	date	n.a.
		PRUCASE	Related use case	nominal	o Implementation o PHD / Follow-up
		DEIDV	Related investigational device	nominal	o Renamic Neo programmer o ECG cable PK-222-L
		DIPRGSNR	Programmer serial number	text	n.a.
		DIECBID	ESG cable ID	nominal	01, 02, ..., 25
		AERELIDV	Adverse Event is related to the investigational device (device related ADE)	nominal	o Not related o Unlikely o Possible o Probable o Causal relationship
		AESER	Adverse Event is serious	nominal	o Yes o No
		AERELSET	Adverse Event is relevant for ADE/DD endpoint	nominal	o Yes o No
CORELSET	Please specify reason for No	text	n.a.		

 analysis set imp SAR = Yes and PRUCASE = Implementation

Data file, identifier record id	Notes	Variable name	Variable label	Variable Level	Nominal values
internal adjudication	Case listing for AETYP = DD	AETYP	Type of event	nominal	o AE o DD
		DERCDT	Date of detection	date	n.a.
		PRUCASE	Related use case	nominal	o Implementation o PHD / Follow-up
		DEIDV	Related investigational device	nominal	o Renamic Neo programmer o ECG cable PK-222-L
		DIPRGSNR	Programmer serial number	text	n.a.
		DIECBID	ESG cable ID	nominal	01, 02, ..., 25
		DEADED	Device efficiency is relevant for ADE/DD endpoint	nominal	o Yes o No
		COADED	Please specify reason for No	text	n.a.

Data file, identifier patient display id full	Notes	Variable name	Variable label	Variable Level	Nominal values
data SAR	descriptive	any ade SAR 	Any Adverse Device Effect (serious or non-serious) based on internal adjudication	nominal	o Yes o No
data SAR	descriptive	any sade SAR 	Any Serious Adverse Device Effect based on internal adjudication	nominal	o Yes o No
data SAR	descriptive	any dd SAR 	Any Device Deficiency	nominal	o Yes o No
data SAR	descriptive	any ade dd SAR 	Any Adverse Device Effect (serious or non-serious) or Device Deficiency based on internal adjudication	nominal	o Yes o No
data SAR	descriptive	n ade SAR 	Number of Adverse Device Effects (serious or non-serious) based on internal adjudication	metric to be reported as nominal	o 1 o 2 ...

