	case listing for QSPSAPAS = Somewhat difficult OR QSPSAPAS = Very difficult including programmer serial number DIPRGSNR (see chapter15.1)	COPSAPAS	NEW: Printing: Please specify Somewhat difficult / Very difficult	text	...
	case listing for QSPGPV = No including programmer serial number DIPRGSNR (see chapter15.1)	COPGPV	NEW: Battery: Please specify in case of NO	text	...
	case listing for QSRGPSA = No including programmer serial number DIPRGSNR (see chapter15.1)	CORGPSA	Please specify in case of NO	text	...
	Case listing for all non-missing data including programmer serial number DIPRGSNR (see chapter15.1)	general comment	General comment	text	...

Data file, identifier patient display id full	Notes	Variable name	Variable label	Variable level	Nominal values
data SAR	case listing for any reported problem: QSPGHPRB, QSRFTPRB, QSSAPRB, QSPRPRB, QSPITPRB, QSDFFPRB, QSPRGPRB, QSDFTPRB contain "Yes"; DUPSAAS = No, QSCNNPRB, QSDEXPPR, QSPRNTPR, QSPRGBPR QSANYPRB contain "Yes"	DIPRGSNR (see chapter 15.1)	Programmer serial number	text	...

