**Renamic Neo and software**

Data file, identifier	Notes	Variable name	Variable label	Variable level	Nominal values
patient display id full & autom SVTYP					
accessory log details	No report	SVTYP	Visit type	nominal	o Implantation o Pre-hospital discharge o Follow-up

Data file, identifier	Notes	Variable name	Variable label	Variable level	Nominal values
patient display id full & SVTYP & helpvar model & DIPRGSNR					
accessory log details (see Analysis Set and Data Selection)	Selection DIPRGM DL = Renamic Neo; no report	DIPRGSNR	Programmer serial number	text	...
		DISFTVER	Programmer software version	nominal	NEO 2004.A ...

Note: In case of any reported problem, the serial number DIPRGSNR of the Renamic Neo, which was used for the specific investigation for a specific patient (or programmers in case more than one programmer were used), will be reported together with the patient id patient display id full.

Data file, identifier	Notes	Variable name	Variable label	Variable level	Nominal values
DIPRGSNR					
renamicneo SAR	descriptive	n imp per renamicneo SAR 	Number of implantations performed with specific Renamic Neo programmer	metric to be reported as nominal	1 2 ...

Data file, identifier	Notes	Variable name	Variable label	Variable Level	Nominal values
patient display id full					
data SAR	descriptive	n renamicneo imp SAR 	Number of Renamic Neo programmers used during implantation	metric to be reported as nominal	1 2 ...
		n renamicneo imp NEO2004A SAR 	Number of Renamic Neo programmers with software NEO 2004.A used during implantation	metric to be reported as nominal	1 2 ...

 Patient-specific data for lead RA model SAR = DIDVTYP = RA lead AND DTDVSTAT = Implanted and active DIDVMDL

 Patient-specific data for lead RV model SAR = DIDVTYP = RV lead AND DTDVSTAT = Implanted and active DIDVMDL

 Patient-specific data for lead LV model SAR = DIDVTYP = LV lead AND DTDVSTAT = Implanted and active DIDVMDL

 Patient-specific data for lead VCS model SAR = DIDVTYP = VCS lead AND DTDVSTAT = Implanted and active DIDVMDL

 Count different patient display id full per DIPRGSNR from accessory log details with SVTYP = Implantation

 Count different DIPRGSNR per patient display id full for SVTYP = Implantation

 Count different DIPRGSNR with DISFTVER = "NEO 2004.A" per patient display id full for SVTYP = Implantation

ECG cable

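### Four SAP rules give wrong or incomplete descriptive output if programmed as written: the failed-programming listing, the follow-up flag, the device-model table and one accessory-bag count

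*SAP*

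**What the plan says.** **(a) Failed programming, SAP chapter 13, Used Programmer Features: Implant.** The item `QSPRGAS` has three categories: programmed successfully, "device not successfully programmed", and not done. The free-text reason `COPRGAS` is to be printed as a "case listing for QSPRGAS = used, but not successfully OR QSPRGPRB = Yes, with Adverse Event OR QSPRGPRB = Yes, without Adverse Event". Chapter 14 repeats the chapter 13 analyses for PHD and follow-up. Protocol 7.5 names "Success of adequate programming of the implant" among the further data of interest.

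**(b) Visit flags, SAP 8.5.** Footnote 11 derives `PHD renamicneo SAR` from PHD visits. Footnote 13 is attached to `FU renamicneo SAR` and tests for a regular follow-up visit, but both of its branches assign `PHD renamicneo SAR`.

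**(c) Device model, SAP 15.1, footnote 29.** The model is taken from rows where the device type is pacemaker AND ICD, OR CRT-P, OR CRT-D, OR ICM. SAP 5.9 keys the device log by patient and device type. Chapter 16 repeats the chapter 15 rules for PHD and follow-up.

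**(d) Accessory bag, SAP 15.1, footnote 59.** The count of bags used without success looks for a usage value in `QSACCBPR`, the problem item. That value belongs to `QSACCBAS`, the usage item.

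**The concern.** The SAP sets out to give detailed instructions for the report, and SAP 1.1 says so. Protocol 7.2.1 states that there is no hypothesis and that all analyses are explorative, so the frequency tables and case listings are the study's performance and usability results. A rule that cannot fire, or that writes to the wrong variable, therefore falls directly on what will be reported.

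Under (a), a failed implant programming could be reported as a count without the investigator's reason. Under (b), one declared output has no derivation and another may be overwritten. Under (c), the two device classes that make up most of the planned implantations are missing from the model table. Under (d), a table entry of 0 could contradict the case listing beside it.

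Protocol 11.8 adds a practical point: deviations from the valid SAP must be indicated in the statistical and clinical reports. A programmer who follows the rules produces wrong output, and one who quietly repairs them creates a deviation to declare.

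**Working it through.** The plan states no figure for these rules, so the check is to apply each one literally and compare it with the evident intent.

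**(a) Programming listing.** `QSPRGAS` has 3 values. `QSPRGPRB` has 4 states: Yes with adverse event, Yes without, no problem detected, missing. That makes 3 × 4 = 12 combinations.
- Literal rule: the `QSPRGAS` condition never holds, so only the two Yes states fire, 3 × 2 = 6 combinations.
- Intended rule (failure or any Yes): those 6, plus failure with no problem detected and failure with the problem item missing, 6 + 2 = 8.
- Missed: 8 − 6 = 2 combinations, both of them failures. The table's footnote rule fills a missing problem item only after success, so it does not rescue the second.
- The neighbouring listings show the intent. The RF telemetry one, for example, is a "case listing for QSRFTAS = used, but not successfully OR QSRFTPRB = Yes, with Adverse Event", and there the failure value does exist for the item tested.

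**(b) Visit flags.** Protocol 9.1 says that implantation and follow-up patients are different patients. Running footnote 11 and then footnote 13:
- implantation patient with a PHD: PHD flag Yes, then No;
- implantation patient without a PHD: No, then No;
- follow-up-only patient: No, then Yes;
- `FU renamicneo SAR`: never assigned.

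In the implantation set the PHD frequency thus reads 0 of 50. In the PHD/FUP set, with x PHD patients and y follow-up patients, it reads y/(x + y) instead of x/(x + y). The synopsis plans about 120 patients, 50 implantations and 100 PHD or follow-up cases. Two splits fit the 100 cases:
- 120 − 50 = 70 follow-up-only patients and 100 − 70 = 30 PHDs: literal 70/100, correct 30/100;
- a PHD for all 50 implantation patients, leaving 100 − 50 = 50 follow-ups: literal 50/100, correct 50/100.

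So the error in that set runs from 0 to 40 percentage points, depending on the split. In the implantation set the correct value would be 30 to 50 of 50.

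**(c) Device model.** One row carries one device type, so pacemaker AND ICD is false on every row. With AND evaluated before OR, CRT-P, CRT-D and ICM rows are kept and pacemaker and ICD rows are lost. If AND is taken to govern the whole OR chain, no row qualifies. Pacemakers and ICDs are lost either way. With the approximate quotas in protocol 8.1.2, under the first grouping:

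| | IPG | ICD | CRT | ICM | Total | Kept | Lost |
|---|---|---|---|---|---|---|---|
| Implantation | 15 | 15 | 20 | none | 50 | 20 | 15 + 15 = 30 |
| PHD/follow-up | 20 | 20 | 40 | 20 | 100 | 40 + 20 = 60 | 20 + 20 = 40 |

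The totals agree with the planned 50 and 100.

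**(d) Accessory bag.** `QSACCBPR` can be Yes with adverse event, Yes without, or no problem detected. None of these is the value that footnote 59 looks for, so the count is 0 for every combination. The parallel footnotes 40, 43, 50 and 56 (ECG cable, electrode clip, patient cable, patient adapter) all use the usage item.

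**The case against.** The strongest reply is that these are proofreading slips whose intent is plain from adjacent text. The category list for `QSPRGAS` stands just before its listing; footnote 13 has the right label and condition; footnote 29 uses OR everywhere else; the bag's own case listing uses the right item. No endpoint, hypothesis or pass/fail criterion depends on them. That stands, and it is why the severity is low.

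On (a), the missed case is narrow: a failure with no problem ticked is close to self-contradictory, and a failure caused by the programmer should also be recorded as a device deficiency (protocol 18.3). A reader might infer that failed programming would vanish from the report, or that the programmer could not be traced. The documents do not support this. The frequency table counts every failure. The serial number can still appear through the "case listing for any reported problem" if another item is positive, the general-comment listing, the "Case listing for AETYP = DD" in SAP 10.2, or the note in 15.1 that begins "In case of any reported problem, the serial number DIPRGSNR of the Renamic Neo, which was used for the specific investigation". None of these prints `COPRGAS`, so the loss is confined to the stated reason.

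On (b), the wrong PHD frequency needs both footnotes to be run unedited and in order, with an empty declared output going unnoticed. PHD and follow-up dates are derived separately in chapter 6 and offer a cross-check. Nor should 50 PHDs be added to 70 follow-up-only patients to size the error: that makes 120 cases, against the 100 planned.

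On (c), a reader might conclude that footnote 29 also wrongly omits the active-implant condition that footnotes 30 to 33 place on leads. No text requires it for devices, and the device-type subgroup rule (footnote 5) has none either. It is an open choice, not an error.

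**Conclusion.** The point holds as a minor correction. Each of the four rules is wrong as written, and each affects descriptive output only.

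- (a) The reason for a failed programming goes unlisted when `QSPRGPRB` is negative or missing. The documents give no expected frequency of this, so its size cannot be estimated.
- (b) `FU renamicneo SAR` is never derived. If footnote 13 is run after footnote 11, the PHD flag is No for every implantation patient, given that none has a regular follow-up. The error in the PHD/FUP set depends on the PHD/follow-up split and can be nil.
- (c) IPG and ICD models drop out: about 30 of 50 implantations and 40 of 100 PHD/follow-up cases. This assumes row-level evaluation, AND before OR, and that the approximate quotas are met.
- (d) One count is fixed at 0.

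A reader might infer a threat to the safety results. There is none here: the ADE/DD flags in chapters 10 and 11 do not use these rules, and the device-type subgroup is intact.

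**What to change.** Amend the SAP as follows:

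- (a) In the `COPRGAS` listing, replace the `QSPRGAS` condition by "device not successfully programmed" and keep the two `QSPRGPRB` conditions. This carries to chapter 14.
- (b) In footnote 13, assign `FU renamicneo SAR` in both branches.
- (c) In footnote 29, replace AND by OR. All five device types are then kept, 50 of 50 and 100 of 100 on the planned mix. This carries to chapter 16.
- (d) In footnote 59, use `QSACCBAS`. This also carries to chapter 16.

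Two editorial corrections can go in at the same time. Footnotes 4 and 8 write `analysis set FUP SAR`, where the table in 7.1 and footnotes 12, 24, 27 and 61 have `analysis set PHD FUP SAR`. The any-problem listing in chapter 13 writes `QSDFFPRB` for the declared `QSDFPPRB`.

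The cost is a few words per rule. Protocol 11.8 allows SAP updates before database freeze or closure. No data collection or patient is affected.
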